6.5 Medical Guidelines for the Treatment of an Overdose

There is no specific treatment for TORISEL[®] intravenous overdose. Temsirolimus has been administered to patients with cancer in phase 1 and 2 trials with repeated intravenous doses as high as 220 mg/m². The risk of several serious adverse events, including thrombosis, bowel

perforation, interstitial lung disease (ILD), seizure, and psychosis, is increased with doses of temsirolimus greater than 25 mg.(Pfizer 2011; Wyeth 2011)

There is no specific treatment for NEXAVAR overdose. The highest dose of sorafenib studied clinically is 800 mg twice daily. The adverse reactions observed at this dose were primarily diarrhea and dermatologic. No information is available on symptoms of acute overdose in animals because of the saturation of absorption in oral acute toxicity studies conducted in animals. In cases of suspected overdose, sorafenib should be withheld and supportive care instituted. (Bayer 2011)

6.6 Dietary Restrictions

Avoid grapefruit and grapefruit juice (may increase levels or toxicity of sirolimus).

Avoid supplements containing St. John's Wort, alfalfa, aloe, bilberry, bitter melon, burdock, celery, damiana, echinacea, fenugreek, garcinia, garlic, ginseng (American), gymnema, marshmallow, stinging nettle.

6.7 Prohibited Medications

6.7.1 Temsirolimus

Temsirolimus is metabolized by CYP3A4 to its active metabolite sirolimus which is a substrate of both CYP3A4 and P-glycoprotein. Temsirolimus also inhibits P-glycoprotein. Temsirolimus has been shown to inhibit CYP2D6 *in vitro*, but no effect is expected *in vivo*. See Appendices 4-7.

CYP3A4 inhibitors

May decrease metabolism of temsirolimus and sirolimus. Strong inhibitors of CYP3A4 are prohibited; other inhibitors should be avoided or used with caution.

CYP3A4 Inducers

May increase metabolism of temsirolimus and sirolimus. All inducers of CYP3A4 are prohibited.

Sensitive CYP3A4 substrates and those with a narrow therapeutic range as defined by FDA are prohibited.

P-glycoprotein inhibitors

May increase serum concentration of temsirolimus and sirolimus which are P-glycoprotein substrates, or alter distribution. **Should be avoided or used with caution.**

P-glycoprotein inducers

May decrease serum concentration of temsirolimus and sirolimus which are P-glycoprotein substrates, or alter distribution. **Should be avoided or used with caution.**

ACE inhibitors

Risk of angioedema may be increased by temsirolimus. May be used with caution.

Cardiac glycosides

Temsirolimus may inhibit transport by P-glycoprotein. **Use is prohibited.**

Herbal/Nutriceutical

Avoid supplements containing St. John's Wort, alfalfa, aloe, bilberry, bitter melon, burdock, celery, damiana, echinacea, fenugreek, garcinia, garlic, ginseng (American), gymnema, marshmallow, stinging nettle.

Vaccines

Temsirolimus may diminish efficacy of vaccination and/or increase risk of toxicity from live vaccines. **Should be avoided** during protocol treatment.

6.7.2 Sorafenib

Sorafenib is metabolized by CYP3A4 and UGT1A9 and has been shown to inhibit CYP2B6, CYP2C8, and CYP2C9 as well as UGT1A1 and UGT1A9. Though inhibition of CYP2C9 has been documented, no effect was observed in an interaction study with warfarin. See Appendices 4-7.

CYP3A4 inhibitors

May increase serum concentration and toxicity of sorafenib. Strong inhibitors of CYP3A4 are prohibited; other CYP3A4 inhibitors should be avoided or used with caution.

CYP3A4 inducers

May decrease serum concentration of sorafenib. All inducers of CYP3A4 are prohibited.

Sensitive CYP3A, CYP2B6, CYP2C8, and CYP2C9 substrates and those with a narrow therapeutic range as defined by FDA are prohibited. (2009)

Other substrates of CYP3A4, CYP2B6, CYP2C8, and CYP2C9 should be avoided or used with caution.

UGT1A1 and UGT1A9 substrates

Sorafenib inhibits UGT1A1 and UGT1A9 and may increase exposure to these drugs; should be avoided or used with caution.

Doxorubicin

Sorafenib has been shown to increase levels of doxorubicin in vitro. Use is prohibited.

Herbal/Nutriceutical

Avoid echinacea and St. John's Wort as well as any herbal products which may interact with CYP3A4 system.

A detailed list of agents that should be **avoided or used with caution** due to risk for interaction with temsirolimus and sorafenib are in Appendices 6-9.

7. Reporting and Documentation of Results

7.1 Evaluation of Efficacy (or Activity)

7.1.1 Measurement of Response and Progression

Target and non-target lesions will be defined by RECIST guidelines (version 1.1): (Therasse, Arbuck et al. 2000) (Eisenhauer, Therasse et al.) All enrolled patients will imaging of chest, abdomen, and pelvis at baseline and after every 2 cycles (8 weeks \pm 7 days) of protocol therapy. RECIST 1.1 measurements will be performed by centralized radiologist at UCSF, without knowledge of patients' clinical responses to protocol therapy, imaging studies during first 6 months on protocol therapy (including post-cycle 6 imaging), then at each study site by qualified investigator and/or radiologist for subsequent studies for patients who remain on protocol therapy. The schedule and methods of radiographic evaluation are described in previous sections.

7.1.1.1 Definitions

Evaluable for toxicity

All patients will be evaluable for toxicity from the time of their first treatment with the study drug. The study will use the CTCAE Version 4.0 for reporting adverse events.

Evaluable for efficacy

All enrolled patients who have received at least one dose of study drug (unless determined to be ineligible and replaced for reasons such as inability to comply or withdrawal of consent) will be evaluable for the primary efficacy endpoint according to the definitions stated below.

7.1.1.2 Disease Parameters

Measurable disease

Measurable disease is defined as lesions (or tumors) that can be accurately measured in at least one dimension (longest diameter to be recorded) with a minimum size of 10mm by CT scan (irrespective of scanner type) and MRI (no less than double the slice thickness and a minimum of 10mm), 10mm caliper measurement by clinical exam (when superficial), and/or 20mm by chest X-ray (if clearly defined and surrounded by aerated lung).

All tumor measurements will be recorded in millimeters or decimal fractions of centimeters. Previously irradiated lesions are considered non-measurable except in cases of documented progression of the lesion since the completion of radiation therapy.

Non-measurable disease

Non-measurable disease is all other lesions (or sites of disease), including small lesions (longest diameter < 20 mm with conventional techniques or < 10 mm using spiral CT scan). Leptomeningeal disease, ascites, pleural or pericardial effusion, inflammatory breast disease, lymphangitic involvement of skin or lung, abdominal masses/abdominal organomegaly identified by physical exam that is not measurable by reproducible imaging techniques are all non-measurable.

Target lesions

All measurable lesions up to a maximum of 5 lesions total (and a maximum of two lesions per organ) representative of all involved organs should be identified as target lesions and recorded and measured at baseline. Target lesions will be selected on the basis of their size (lesions with the longest diameter) and their suitability for accurate repeated measurements (either by imaging techniques or clinically). A sum of the longest diameter (LD) for all target lesions will be calculated and reported as the baseline sum LD. The baseline sum LD will be used as reference by which to characterize the objective tumor response.

Non-target lesions

All other lesions (or sites of disease) including any measurable lesions over and above the 5 target lesions should be identified as non-target lesions and should also be recorded at baseline. It is possible to record multiple non-target lesions involving the same organ as a single item on the case record form (e.g. "multiple enlarged pelvic lymph nodes" or "multiple liver metastases"). Measurements of these lesions are not required, but the presence or absence of each will be noted throughout follow-up.

7.1.1.3 Methods for Evaluation of Measurable Disease

All measurements will be taken and recorded in metric notation using a ruler or calipers. All baseline evaluations will be performed as closely as possible to the beginning of treatment and never more than 28 days before the beginning of the treatment.

The same method of assessment and the same technique will be used to characterize each identified and reported lesion at baseline and during follow-up. Imaging-based evaluation is preferred to evaluation by clinical examination when both methods have been used to assess the antitumor effect of a treatment.

Conventional CT and MRI

These techniques should be performed with cuts of 10 mm or less in slice thickness contiguously. Spiral CT should be performed using a 5 mm contiguous reconstruction algorithm. This applies to tumors of the chest, abdomen, and pelvis. Triphasic imaging of abdomen should be obtained when feasible.

Cytology, Histology. These techniques can be used to differentiate between partial responses (PR) and complete responses (CR) in rare cases (e.g., residual lesions in tumor types, such as germ cell tumors, where known residual benign tumors can remain).

The cytological confirmation of the neoplastic origin of any effusion that appears or worsens during treatment when the measurable tumor has met criteria for response or stable disease is mandatory to differentiate between response or stable disease (an effusion may be a side effect of the treatment) and progressive disease.

7.1.1.4 Response Criteria

Evaluation of Target Lesions

Complete Response (CR)

Disappearance of all target lesions, determined by two separate observations conducted not less than 4 weeks apart. Any pathological lymph nodes (whether target or non-target) must have reduction in short axis to <10 mm (the sum may not be "0" if there are target nodes). There can be no appearance of new lesions.

Partial Response (PR)

At least a 30% decrease in the sum of the longest diameter (LD) of target lesions, taking as reference the baseline sum LD. There can be no appearance of new lesions.

Progressive Disease (PD)

At least a 20% increase in the sum of the SLD of target lesions, taking as reference the smallest sum SLD recorded since the treatment started and minimum 5 mm increase over the nadir, or the appearance of one or more new lesions.

Stable Disease (SD)

Neither sufficient shrinkage to qualify for PR nor sufficient increase to qualify for PD, taking as reference the smallest sum LD since the treatment started.

Evaluation of Non-Target Lesions

Complete Response (CR)

Disappearance of all non-target lesions and normalization of tumor marker level. All lymph nodes must be non-pathological in size (< 10 mm short axis).

Incomplete Response/Stable Disease (SD)

Persistence of one or more non-target lesion(s) and/or maintenance of tumor marker level above the normal limits.

Progressive Disease (PD)

Appearance of one or more new lesions and/or unequivocal progression of existing non-target lesions.

Evaluation of Best Overall Response

The best overall response is the best response recorded from the start of the treatment until disease progression/recurrence (taking as reference for progressive disease the smallest measurements recorded since the treatment started). The patient's best response assignment will depend on the achievement of both measurement and confirmation criteria.

Table 3.1.1.4 Response Criteria

Target Lesions	Non-Target Lesions	New Lesions	Overall Response	Best Response for this Category Also Requires
CR	CR	No	CR	> 4 weeks confirmation
CR	Non-CR/ Non-PD	No	PR	> 4 weeks confirmation
PR	Non-PD	No	PR	
SD	Non-PD	No	SD	documented at least once > 4 weeks from baseline
PD	Any	Yes or No	PD	no prior SD, PR or CR
Any	PD*	Yes or No	PD	
Any	Any	Yes	PD	

* In exceptional circumstances, unequivocal progression in non-target lesions may be accepted as disease progression

Duration of Response

Duration of overall response

The duration of overall response is measured from the time measurement criteria are met for CR or PR (whichever is first recorded) until the first date that recurrent or progressive disease is objectively documented (taking as reference for progressive disease the smallest measurements recorded since the treatment started).

The duration of overall CR is measured from the time measurement criteria are first met for CR until the first date that recurrent disease is objectively documented.

Duration of stable disease

Stable disease is measured from the start of the treatment until the criteria for progression are met, taking as reference the smallest measurements recorded since the treatment started.

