* Patients will be followed every 3-6 months for up to 5 years after study discontinuation or until death, at standard-of-care clinic visits with treating investigator or by telephone calls from treating investigator or a designated study coordinator (± 3 months)

¹ May start study prior to obtaining specimens if pathology report is available

² Confirmation of antiviral therapy with an appropriate antiviral agent for HBV is required in patients with positive hepatitis B surface antigen, HBcAb IgM, and/or viral load

³ Sorafenib will be taken orally twice daily at starting dose with modifications per Section 5.2.3

⁴ Weight and vital signs on Days 8, 15, 22 of Cycle 2 and future cycles

⁵ Disease assessment including Child-Pugh, BCLC, and CLIP scores

⁶ Evaluation of clinical response or deterioration at Follow-Up Visit: overall survival will be measured from time of first dose of therapy to date of death, evaluation of any residual symptomatic adverse events (if applicable), other anti-cancer therapies

⁷ Complete metabolic panel (electrolytes, BUN, creatinine, glucose, calcium, magnesium, phosphorus, total and direct bilirubin, alkaline phosphatase, albumin, AST, and ALT)

⁸ Prothrombin time/ international normalized ratio (PT/INR)

⁹ Hepatitis B viral DNA quantitative in patients with positive hepatitis B viral load at baseline (Screening) and/or positive HBsAg, HBcAb total, and/or HBcAb IgM (odd cycles only or more frequently at investigator's discretion), and end of treatment if not measured within 4 weeks prior.

¹⁰ Screening and Day 1 of odd cycles only (Cycle 3, 5, 7, etc.)

¹¹ Initiate standing phosphate repletion for patients with baseline ≥ Grade 2 hypophosphatemia; adjust dosage as clinically indicated at each visit

¹² CTC on Day 1 of Cycles 1, 2 & 3 only. See Study Laboratory and Procedures Manual for instructions

¹³ Banking blood samples on Cycle 1 Day 1, Cycle 1 Day 8, and Cycle 3 Day 1, and at End of Treatment (if not done within 4 wks). See Study Laboratory and Procedures Manual for instructions

¹⁴ Odd cycles only, every 8 weeks ± 7 days, starting Cycle 3, Day 1

¹⁵ If not done within 8 weeks, imaging with CT chest (with or without contrast) plus triphasic CT abdomen and pelvis with intravenous contrast or triphasic gadolinium-enhanced MRI abdomen/pelvis

¹⁶ May use values from >28 days from registration

¹⁷ Temsirolimus infusion may be performed within ± 3 days

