7.1.1.5 Centralized Review of Radiology

Radiographic assessments will be performed by a Radiologist at UCSF without knowledge of patients' clinical responses to protocol therapy for all patients' imaging studies during the first 6 months' on therapy (including imaging after completion of cycle 6). For patients enrolled on study at the Robert H. Lurie Comprehensive Cancer Center of Northwestern University, standard CT or MRI images will be acquired at that study site, stored on a CD as DICOM images, and shipped via FEDEX to the designated UCSF study coordinator. After cycle 6 imaging, RECIST 1.1 measurements may be performed at the treating site by a qualified investigator or radiologist. See Study Laboratory and Procedures Manual for detailed instructions.

Initial assessment of response or progression may be made based upon standard of care Radiology review plus clinical assessment if RECIST 1.1 measurements are not available at the time of study visit. In patients without signs of clinical progression, progression must be confirmed by RECIST 1.1 prior to removal from study. If progression is identified by RECIST 1.1 that was not identified by standard of care Radiology review plus clinical assessment, a patient will be removed from study at date of next scheduled study visit. Efforts will be made to obtain RECIST 1.1 measurements for patients treated at both sites within approximately 7 days of start of odd cycles.

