9.1.2 Primary Endpoint

Median TTP will be calculated in months from date of first dose of protocol therapy to date of removal from study for radiographic (per RECIST 1.1) and/or clinical progression including death attributed to progression. For patients removed from study for other reasons than progression (such as toxicity, withdrawal of consent, or death from other causes than documented radiographic and/or clinical progression), TTP will be censored at the date last known to be progression-free.

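### Section 7.1.1.4 gives two rules for unequivocal non-target progression, and applying the footnote literally can delay the primary TTP event to a later scan

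*Combined protocol and SAP*

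**What the plan says.** Three statements in Section 7.1.1.4 cover the same finding.

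- **Definition.** PD for non-target lesions is "Appearance of one or more new lesions and/or unequivocal progression of existing non-target lesions". No condition is attached.
- **Table row.** In the response table, the row with any target status, non-target PD (starred) and new lesions yes or no gives an overall response of PD.
- **Footnote to the star.** "In exceptional circumstances, unequivocal progression in non-target lesions may be accepted as disease progression". The text does not say what makes circumstances exceptional or who decides.

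Other sections carry the classification through to the primary endpoint.

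- Section 7.1.1.5: in patients without signs of clinical progression, "progression must be confirmed by RECIST 1.1 prior to removal from study".
- Section 9.1.2: TTP runs to "date of removal from study for radiographic (per RECIST 1.1) and/or clinical progression including death attributed to progression".
- Table 6.1, imaging footnote: "Odd cycles only, every 8 weeks ± 7 days, starting Cycle 3, Day 1".
- Section 7.1.1.2 allows at most five target lesions and "a maximum of two lesions per organ". Lesions beyond that limit are non-target.
- Sections 7.1.1 and 7.1.1.5: a radiologist at the coordinating site, unaware of clinical response, reads all scans up to and including the one after cycle 6. Thereafter: "After cycle 6 imaging, RECIST 1.1 measurements may be performed at the treating site by a qualified investigator or radiologist".

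**The concern.** Take a patient whose two liver target lesions are stable, while a third liver lesion that was present at baseline has clearly grown. There is no new lesion and no clinical decline. Under the definition and the table row this is PD at that scan. Under the footnote it is not PD unless someone judges the case exceptional. Two careful readers can therefore classify the same scan differently and both follow the protocol.

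The classification sets the TTP event date. Compared with the definition, the footnote can only withhold or postpone an event. In a single-arm trial judged against a fixed 3-month null, a postponed event favours the combination. With two targets allowed per organ, patients with several liver lesions at baseline will carry non-target liver disease, so the situation need not be rare.

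**Working it through.** **Inputs from the documents**

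- Section 9.2.1: n = 25, one-sided 10% level, power 88%, exact test of 25% versus 50% at 6 months, TTP roughly exponential, null median 3 months, alternative 6 months.
- Section 9.4.2: the primary summary is the Kaplan-Meier median TTP; the proportion with TTP of at least 6 months is also reported.
- Scans every 8 weeks ± 7 days.

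**Assumptions not in the documents**

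- f, the share of progressions first seen only in non-target lesions: 5% to 30%.
- Every such case is refused as PD and called exactly one scan late.
- The cutoff of 10 successes in 25, inferred below.

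**1. Reproduce the stated design.** Exact binomial, n = 25:

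| Cutoff | P(success), p = 0.25 | P(success), p = 0.50 |
|---|---|---|
| ≥ 9 | 0.149 | 0.946 |
| ≥ 10 | 0.071 | 0.885 |
| ≥ 11 | 0.030 | 0.788 |

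The smallest cutoff within the 10% level is 10 of 25. Its power is 88.5%, which matches the stated 88%.

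**2. Length of the delay.** Eight weeks is 8 × 12/52.18 = 1.84 months. With 7 days' leeway at each end, the interval is 42 to 70 days (1.4 to 2.3 months). Scans fall at 1.84, 3.68, 5.52 and 7.36 months. A progression visible at week 24 (5.52 months) but first accepted at week 32 (7.36 months) crosses the 6-month landmark.

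**3. Patients exposed at the landmark, under the null.** With S(t) = 2^(−t/3):

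- S(16 weeks) = 0.427
- S(24 weeks) = 0.279
- difference = 0.148

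So 14.8% of patients progress between weeks 16 and 24.

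**4. Effect on the 6-month test.** Hold the protocol's null rate at 25% and add the delayed cases: p = 0.25 + f × 0.148.

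| f | p | P(≥ 10 of 25) under the null |
|---|---|---|
| 0 | 0.250 | 7.1% |
| 5% | 0.257 | 8.4% |
| 10% | 0.265 | 9.9% |
| 20% | 0.280 | 13.3% |
| 30% | 0.294 | 17.3% |

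The nominal 10% is passed only just above f = 10%.

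**5. Effect on the scan-based median, under the null.** S(8 weeks) = 0.654. The recorded progression-free share at week 16 is 0.427 + f × (0.654 − 0.427). At f = 30% this is 0.495, still below one half, so the median stays at week 16. It reaches 0.5 when f = (0.5 − 0.4273)/(0.6537 − 0.4273) = 0.32.

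**The case against.** The definition and the table row agree and only the footnote departs, so many readers would simply call PD. Four points limit the consequence, and they stand.

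- **The median is robust.** The headline primary summary is the Kaplan-Meier median, which on the scan grid does not move anywhere in the assumed range. The effect falls on the 6-month proportion, which underlies the power statement.
- **There are other routes to an event.** Clinical progression counts as a TTP event in its own right, and a new lesion is PD whatever the footnote says. A reader might infer that every additional liver nodule falls under the footnote. That is true only of lesions present at baseline.
- **Reading is central where the landmark is decided.** Scans up to week 24 go to the central radiologist. A reader might infer that central and site readers could disagree on those scans, but the documents give site readers only later ones. Central reading does not settle which rule applies, however, and a case refused at week 24 could be judged at week 32 by a different reader.
- **The driver is assumed.** No document gives f, and the footnote permits acceptance, so refusal in every case is the strictest reading.

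A reader might also start from the week-24 scan and report an error rate of 13.2% rising to 26.9% at f = 30%. The 13.2% is not caused by the footnote. It arises because that scan falls at 5.5 months, where the null progression-free share is 27.9% instead of 25%.

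**Conclusion.** The conflict is in the current text and reaches the primary endpoint. For patients without clinical progression or a new lesion, following the footnote as written gives a later event date than following the definition. The bias has one direction, towards longer TTP.

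Its size is uncertain. If the event moves to the next scheduled scan, the delay is about 1.8 months for an affected patient. It could be shorter if clinical progression intervenes, or longer if target lesions stay stable and no new lesion appears. The range of 8.4% to 17.3%, against 7.1% with no delay, is a sensitivity range. It rests on an assumed f of 5% to 30%, refusal of every such case, a delay of one scan and an inferred cutoff.

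A reader might conclude that the sample-size calculation is wrong or that the median TTP will be visibly inflated. Neither is supported: the 88% power reproduces, and the scan-based null median holds until f exceeds about 32%. The point is worth correcting because the remedy is small and the error is one-sided.

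**What to change.** Reconcile the footnote with the definition and the table row, so that a single non-target PD rule is used for endpoint adjudication by central and site readers alike. The simplest way is to remove the footnote, since the other two statements already agree. Do this before scans are read.

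RECIST progression also leads to removal from treatment (Sections 3.4 and 7.1.1.5). The sponsor must therefore reconcile the same passages for that purpose too; this review takes no position on the treatment rule.

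The cost is one line of text. Some progressions will be recorded earlier than under the footnote, so TTP will be slightly shorter. The stated sample size, level and power do not change.
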